## 7.5 Pharmacokinetic (PK) Analysis

PK analysis will be performed on PK population.

Individual plasma PK parameters, including area under the concentration-time curve (AUC0-12), terminal elimination half-life (t1/2), maximum plasma concentration (Cmax), time to reach maximum plasma concentration (Tmax), elimination rate constant (Kel) and clearance (Cl) will be summarized and presented as described for continuous variables. Along with mean, SD, median and geometric mean concentration (GMC) and 95% GMC will also be provided by treatment arms.

Pharmacokinetic analysis will be performed only if sufficient patient's data are available.

## 8.0 SAFETY & TOLERABILITY ASSESSMENT ANALYSIS

The analysis of safety assessments in this study will include summaries of the following categories of safety data collected for each subject

- ☐

- ☐ Adverse Events

- ☐ Physical Examination

**Title: Statistical Analysis Plan-Module I**

 SOP Number:  
 JSS-DM-BIS-01

Current Version Number: 1.0

Previous Version Number: Nil

 Document Date:  
 25MAR2021

Vital Sign

ECG Record

Laboratory Test

Treatment emergent adverse events (AEs) and serious adverse events (SAEs) will be reported by frequency analysis with respect to incidence, severity as well as seriousness. Clinically significant alterations in clinical laboratory parameters, vital signs and ECG will be reported.

All safety parameters (e.g. AEs, physical examination, vital signs, ECG parameters, Laboratory evaluations) will be summarized descriptively and by treatment. Continuous variables will be described by number (n) of non-missing observations, arithmetic mean, standard deviation, standard error, median and 95%CI. Categorical variables will be described by frequency tables (counts and percentages), however in case of very low occurrences instead of tables with zero proportions, note statement will be added in respective section of table. Safety evaluations will be done on safety population. No formal statistical testing will be performed on the safety data.

### 8.1 Adverse Events

AEs will be coded using the Medical Dictionary for Regulatory Activities (MedDRA). The number and percentages of patients experiencing AEs will be tabulated by system organ class (SOC), preferred term, maximum severity, and relationship to AUR101. Summaries of the number of patients with DLTs, dose reductions/interruptions, SAEs, treatment-related AEs, AEs resulting in treatment/trial discontinuation, and deaths will be presented by dose cohort.

### 8.2 Physical Examination

The baseline medical history of subjects includes information regarding physical history for different body systems (General Appearance, Skin, Neck, Eyes, Lungs etc.). Weight will be recorded at every visit except visit 3, 5 and follow up visit. Height will be captured at screening only. Change in weight and BMI from baseline will be calculated and descriptive statistics (Mean, SD, SE, median) will be presented in dose-wise groups. For rest of the physical examination data, a listing will be presented

### 8.3 Vital Signs

**Title: Statistical Analysis Plan-Module I**

 SOP Number:  
 JSS-DM-BIS-01

Current Version Number: 1.0

Previous Version Number: Nil

 Document Date:  
 25MAR2021

Standard vital signs will include the blood pressure, pulse rate, respiratory rate, and body temperature. Vital signs at each visit and the change from baseline to each post-baseline assessment will be summarized using descriptive statistics.

These parameters will be analyzed using number (n) of non-missing observations, mean, standard deviation (SD), SE, median and 95%CI. Change from baseline in vital sign parameters will also be reported.

#### 8.4 ECG

Overall interpretation of 12 lead ECG will contain within normal limits, abnormal but not clinically significant, or abnormal and clinically significant categories.

The ECG data will be analyzed by treatment groups at each visit using frequency count and percentage of subjects by treatment groups.

#### 8.5 Laboratory Parameters

The laboratory parameters will include Hematology, Liver function Test, and Renal Function Test samples by visits.

The categorical variables will be analyzed using frequency count and percentage of subjects, and continuous variables will be analyzed using number (n) of non-missing observations, mean, standard deviation, SE and median (IQR) by groups. Any change from baseline in laboratory parameters in terms of normal or abnormal (clinically significant or not significant) findings will also be reported through shift tables for overall data without mentioning the groups. Descriptive statistics (Mean, median, SD, SE and 95% CI) will be presented for change from baseline to the respective visit.

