9.2.3 Clinical Laboratory Test

A blood sample will be taken for measurement of hematology and biochemistry parameters, and a urine sample will be taken for urine analysis at the following time points:

- Screening visit
- Randomization visit (Visit 2)
- Week 4, 8 and 12 (Visits 4, 6 and 7)
- Follow-up visit

In addition, viral serology tests will be performed at the screening visit. Following parameters (Table 6) will be measured:

Haematology	Biochemistry
Red blood cells	Alkaline phosphatase
White blood cells (WBCs)	ALT
Differential WBC count (absolute	AST
and %) including neutrophils,	Potassium
eosinophils, basophils, monocytes,	Serum Creatinine
lymphocytes	BUN
Haemoglobin	Sodium
Haematocrit	Chloride
Platelets	Bicarbonate
Mean corpuscular haemoglobin	Phosphorus
MCH concentration	Calcium
Mean corpuscular volume	Total bilirubin
	Albumin
	Globulin
	Total Protein
	Albumin/Globulin ratio
	Glucose
Urinalysis (on Visit 2 and visit 7 only	v)
Routine & microscopic examination	
Viral serology (For screening only)	
HBsAg, hepatitis C antibody, HIV I, H	IIV II

Table 6: List of Clinical Laboratory Tests

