11.7.3 Clinical Laboratory Tests

Clinical laboratory test results will be summarized by treatment groups using descriptive statistics and will include hematology, chemistries, and urinalysis. Laboratory test values which are outside the normal range will be flagged as H (above high normal limit), L (below low normal limit), or A (abnormal) in the data listings. Laboratory values deemed clinically significant by the Investigator should be reported as AEs.

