**Table 3. Study Activities**

Assessment	Screening visit (Up to Day -14)	Treatment Period						Follow-up visit: 14 ± 2 days after last dose
		Visit 2: Randomization visit (Day 1)	Visit 3: Week 2 ± 2 days	Visit 4: Week 4 ± 2 days	Visit 5: Week 6 ± 2 days	Visit 6: Week 8 ± 2 days	Visit 7 (End of Treatment): Week 12 ± 4 days	
Informed Consent	X							
Demographics	X							
Height (Only at Screening), BMI (only at screening), weight	X	X		X		X	X	
Medical history	X	X	X	X	X	X	X	X
Menstrual history in females	X							
Prior/concomitant medication check	X	X	X	X	X	X	X	X
Physical examination	X	X	X	X	X	X	X	X
Vital signs a	X	X	X	X	X	X	X	X
QuantiFERON TB-Gold test b	X							
Inclusion & exclusion criteria check	X							
Inclusion & exclusion criteria verification		X						
12 lead ECG	X							X
Randomization		X						
Photographs of lesions		X	X	X	X	X	X	X
Blood sampling for PK c				X				
Clinical laboratory tests (Haematology, Biochemistry)	X	X		X		X	X	X
Urinalysis		X					X	
Viral Serology	X							
PASI score, IGA by independent evaluator and Investigator	X	X	X	X	X	X	X	X
DLQI		X	X	X	X	X	X	X
IP dispense d		X	X	X	X	X		
IP return and compliance check			X	X	X	X	X	

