### 9.0 REPORTING CONVENTIONS

#### 9.1 Reporting of Numeric Values

All data will be presented by treatment group. Where appropriate, data will be presented including a total overall column and by visit in addition to treatment group.

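### SAP 8.5 names only haematology, liver and renal tests, so the by-arm summaries of glucose, urinalysis and possibly electrolytes that Protocol 11.7.3 promises are left unspecified

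*SAP*

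**What the plan says.** Protocol 11.7.3 sets the commitment: "Clinical laboratory test results will be summarized by treatment groups using descriptive statistics and will include hematology, chemistries, and urinalysis". Protocol Table 6 lists the analytes. Its biochemistry column has 17 items, including glucose and six electrolytes or minerals. Urinalysis has its own entry: "Urinalysis (on Visit 2 and visit 7 only".

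The SAP's own schedule (Table 3) keeps both, with one row for "Clinical laboratory tests (Haematology, Biochemistry") and a separate row for urinalysis.

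SAP 8.5 then describes the laboratory analysis: "The laboratory parameters will include Hematology, Liver function Test, and Renal Function Test samples by visits". It names neither biochemistry as a whole nor urinalysis. The same section pools its normal/abnormal shift tables over the arms, with no group shown.

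Two general rules surround it. SAP 8.0 says: "All safety parameters (e.g. AEs, physical examination, vital signs, ECG parameters, Laboratory evaluations) will be summarized descriptively and by treatment". It adds: "No formal statistical testing will be performed on the safety data". SAP 9.1 says: "All data will be presented by treatment group".

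**The concern.** SAP 8.5 is the only place that says what goes into the laboratory tables, and its list is shorter than the protocol's. A programmer who builds tables from that list has no instruction to produce glucose or urinalysis, and must guess about the electrolytes.

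Safety and tolerability is the first-listed secondary objective. The one completed human study that the protocol describes gave repeated doses to healthy volunteers for 14 days, whereas this trial treats patients for 12 weeks. A modest group-level drift in glucose or an electrolyte would be seen in change-from-baseline tables by arm. It may not be seen in individual cases, since each value can stay unremarkable. The schedule already collects the samples, so the only thing at risk is the summary.

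**Working it through.** The plan gives no figure to reproduce, and no power or error-rate calculation bears on the point. The check compares the texts and counts Table 6 by hand.

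**Step 1. Scope in each place.**

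| Place | Haematology | Biochemistry | Urinalysis |
|---|---|---|---|
| Protocol 11.7.3 (analysis) | yes | all chemistries | yes |
| Protocol Table 6 (collection) | yes | 17 items | Visits 2 and 7 |
| SAP Table 3 (schedule) | yes | yes | yes |
| SAP 8.5 (analysis) | yes | liver and renal tests only are named | not named |

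**Step 2. Sort the 17 biochemistry items.** Neither document defines the liver or renal panel by analyte, so this grouping is an assumption.

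- Liver-type, 8: alkaline phosphatase, ALT, AST, total bilirubin, albumin, globulin, total protein, albumin/globulin ratio.
- Renal-type, 2: serum creatinine, BUN.
- Electrolytes and minerals, 6: potassium, sodium, chloride, bicarbonate, phosphorus, calcium.
- Glucose, 1.
- Check: 8 + 2 + 6 + 1 = 17.

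**Step 3. Count what falls outside the panels named in SAP 8.5.**

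- Electrolytes and minerals counted as renal tests: 17 − (8 + 2 + 6) = 1 item, glucose.
- Electrolytes and minerals not counted as renal tests: 17 − (8 + 2) = 7 items.
- Urinalysis is outside in both cases. It has its own entry in Table 6 and its own row in the schedule, so it does not read naturally as part of a blood-based renal panel. SAP 8.6 gives the urine pregnancy test an output, but no SAP section gives one to urinalysis.

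**Step 4. Look for a declared change.** The SAP contents list an entry 5.6 on changes from the protocol, but the body goes from 5.5 to 6.0 without that section. Where the SAP adds PASI 90 and PASI 100 (SAP 3.2.5), it says openly that the protocol does not contain them. It says nothing similar about laboratory scope.

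**Step 5. Check whether the general rules fill the gap.** SAP 8.0 and 9.1 say how laboratory data are shown (by treatment), not which analytes are tabulated. SAP 8.5 already departs from both rules by pooling its shift tables, so it cannot be assumed to give way to them.

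**The case against.** A reader might take SAP 8.5 as a closed list and conclude that glucose, urinalysis and electrolytes will never be compared with placebo, or that the tables cannot show a shift. The documents do not support that, for these reasons:

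- SAP 8.5 uses the verb *include* and contains no word of exclusion. Protocol 11.7.3 uses the same verb. SAP section 8 is loosely drafted elsewhere: SAP 8.3 lists respiratory rate among the vital signs, which the protocol does not.
- SAP 8.0 and 9.1 still call for laboratory evaluations, and all data, by treatment. SAP 5.4 refers to a biochemistry panel and to summarising out-of-range laboratory values as observed.
- No safety variable is formally tested, so no planned test against placebo is lost.
- Clinically significant laboratory changes are recorded as adverse events (Protocol 10.1 and 11.7.3) and so reach the adverse event summaries in SAP 8.1. Protocol 11.7.3 also flags out-of-range values in the listings.
- The documents describe no glucose, electrolyte or urine signal. The adverse laboratory findings in dogs were hepatic, and liver tests are named in SAP 8.5. The Phase I study reported no remarkable effect on any laboratory parameter.

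All of this stands, and it limits the point to under-specified descriptive summaries. It does not remove the mismatch. The adverse event route catches individual values judged clinically significant, not a shift in the group mean, and the general rules do not say which analytes to tabulate.

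**Conclusion.** The concern holds in limited form. SAP 8.5 is narrower than Protocol 11.7.3, and no change from protocol is declared. The by-arm descriptive summary of glucose and urinalysis is not specified and could be omitted. So could that of the six electrolytes and minerals, if they are not treated as renal tests.

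The size is 1 to 7 of 17 biochemistry items, plus urinalysis. The upper figure should not be quoted alone, because it depends on a panel grouping that the documents do not give. The range also counts the three protein measurements and their ratio as liver tests; a narrower liver panel would widen it. For urinalysis, Table 6 and the schedule give one baseline and one post-baseline assessment (Visits 2 and 7).

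The primary efficacy analysis and the adverse event tables are unaffected. This is a correction worth making because the protocol already promises the output and the data are already scheduled for collection.

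**What to change.** Replace the first sentence of SAP 8.5 with: *All haematology, biochemistry and urinalysis parameters listed in Protocol Table 6 will be summarised by visit and treatment arm, with change from baseline for continuous parameters and counts for urinalysis results.*

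In the same section, present the shift tables by treatment arm. Otherwise normal-to-abnormal shifts would still not be shown by arm for any analyte, including those in the named panels. With both edits, SAP 8.5 agrees with SAP 8.0, SAP 9.1 and Protocol 11.7.3.

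If the shorter list is intended, the SAP should declare it as a change from protocol and give the reason.

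The cost is a small text edit and a few more runs of the same table program. No new data are needed.

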11.4 Description of Statistical Analyses

11.4.1 General Considerations

Data will be summarized using descriptive statistics (number of patients, mean, median, standard deviation, minimum, and maximum) for continuous variables and using frequencies and percentages for discrete variables. Data will be presented by treatment arms.

A comprehensive statistical analysis plan (SAP) will be finalized prior to final data analysis.

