reported accordingly. For abnormal observed value we further summarized as clinically significance and non- clinically significance.

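### SAP 8.5 pools the laboratory shift tables over the arms, against the SAP's own by-arm rule, and leaves out minimum and maximum

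*SAP*

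**What the plan says.** SAP 8.5 plans three kinds of laboratory output.

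- Values by arm: "continuous variables will be analyzed using number (n) of non-missing observations, mean, standard deviation, SE and median (IQR) by groups", with counts and percentages for categorical variables.
- Shift tables for movement between normal and abnormal (clinically significant or not), which "will also be reported through shift tables for overall data without mentioning the groups".
- Mean, median, SD, SE and 95% CI of change from baseline at each visit. That sentence does not state the grouping.

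The surrounding rules point the other way on the shift tables. SAP 9.1: "All data will be presented by treatment group", with a total column as an addition where appropriate. SAP 8.0 says that safety parameters, laboratory evaluations included, "will be summarized descriptively and by treatment". Protocol 11.7.3: "Clinical laboratory test results will be summarized by treatment groups using descriptive statistics and will include hematology, chemistries, and urinalysis". For ECG, which uses the same kind of categories, SAP 8.4 says: "The ECG data will be analyzed by treatment groups at each visit using frequency count and percentage of subjects by treatment groups".

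On the statistics themselves, Protocol 11.4.1 says: "Data will be summarized using descriptive statistics (number of patients, mean, median, standard deviation, minimum, and maximum) for continuous variables". SAP 8.5 gives neither minimum nor maximum. SAP 5.0, 6.0 (general considerations), 8.0, 8.3 and 9.1 omit them too.

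**The concern.** The trial compares two doses with placebo so that risk and benefit can be weighed for each dose and a Phase III dose chosen (Protocol 3.4.1). A shift table pooled over the three arms cannot contribute to that comparison. The instruction in 8.5 is specific and the by-arm rules are general, so a programmer would probably follow 8.5.

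The liver is where this matters most. In the 13-week dog study, ALT/AST rises were adverse at the top dose, and mild, reversible and non-adverse at the no-adverse-effect dose (Protocol 3.2.3). The exposure margin at 600 mg BID is 364160/142764 = 2.55 (Protocol Table 4). Phase 1 found no remarkable effect on liver function, but its longest dosing was 14 days (Protocol 3.3), against 12 weeks here.

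The shift table is also the planned output that separates new abnormalities from old ones. Exclusion criterion 10 starts at 1.5 x ULN for ALT, AST, ALP and total bilirubin, so patients can enter with values already above ULN.

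**Working it through.** The plan states no figure on this point. The check compares the texts and then asks what the remaining by-arm outputs can and cannot show. All counts of events below are assumptions. The arm size of 30 is from Protocol 11.1.

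**1. Texts side by side**

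| Output | Grouping stated | Source |
|---|---|---|
| All data | by treatment group, total in addition | SAP 9.1 |
| Safety parameters, including laboratory | by treatment | SAP 8.0 |
| Laboratory results | by treatment groups | Protocol 11.7.3 |
| ECG categories | by treatment groups | SAP 8.4 |
| Laboratory shift tables | overall only | SAP 8.5 |

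The conflict with SAP 8.0 and 9.1 is direct. Protocol 11.7.3 does not name shift tables, so the conflict there is with its general rule.

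**2. What pooling hides.** If k patients shift, the number of ways to split them over three arms is C(k+2, 2), and the pooled table is the same for every split. The last column puts all k on one dose and none on placebo. Fisher's two-sided p is only a yardstick, since SAP 8.0 plans no safety testing.

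| k assumed | Pooled table | Possible splits | Extreme split v placebo |
|---|---|---|---|
| 3 | 3/90 (3.3%) | 10 | 3/30 v 0/30, p = 0.24 |
| 6 | 6/90 (6.7%) | 28 | 6/30 v 0/30, p = 0.024 |
| 9 | 9/90 (10.0%) | 55 | 9/30 v 0/30, p = 0.002 |

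An even split gives p = 1.0 in each row.

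**3. Do by-visit abnormal counts replace the shift table?** With b abnormal at baseline and v at a visit among n, new cases lie between max(0, v − b) and min(v, n − b). For b = 5, v = 8, n = 30, this is max(0, 3) = 3 to min(8, 25) = 8. The count does not fix the number of new cases.

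**4. Do mean, SD and median (IQR) show individual rises?** Assume 30 ALT values evenly spread from 0.3 to 1.0 x ULN, with the highest patients then rising.

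- With up to 7 of 30 raised to 3, 5 or 8 x ULN, the median (0.65) and quartiles (0.47, 0.83) do not move.
- One patient at 8 x ULN: mean 0.88, mean change 0.23, SD of change 1.28.
- Two patients at 5 x ULN: mean 0.92, mean change 0.27, SD of change 1.02.

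Mean and SD respond to a rise but do not identify its peak or the number of patients. As a bound with no distribution assumed, n = 30 with known mean and SD allows a largest change from 1/√30 = 0.18 to 29/√30 = 5.29 SD above the mean. The maximum, which Protocol 11.4.1 lists, would settle this at each visit.

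**5. Joint rises.** If A patients have raised ALT and B raised bilirubin among 30, the number with both lies between max(0, A + B − 30) and min(A, B). For 3 and 3, it is 0 to 3.

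**The case against.** The strongest reply is that much by-arm information survives, and most of that reply stands.

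- SAP 8.5 gives means, SDs, medians and quartiles by arm. Change from baseline is by arm if SAP 8.0 and 9.1 are followed. These show the average size of change.
- SAP 5.4 adds: "For abnormal observed value we further summarized as clinically significance and non- clinically significance". With SAP 8.0 and 9.1, this is most naturally read as by-arm counts of abnormal values. An excess such as 6/30 on one dose would usually show there, unless the rises were transient, spread over visits or offset by baseline cases that resolved.
- Values judged clinically significant are reported as adverse events (Protocol 11.7.3). Treatment-emergent events must be new or worsened (Protocol 11.7.1), and SAP 8.0 puts adverse events by treatment. New or worsened significant cases are therefore already separated by arm. Entry does rest on investigator judgement, and severity is graded by effect on daily activities (Protocol 10.1.1), so these tables give neither size nor peak.
- Listings flag each out-of-range value (Protocol 11.7.3). With 30 patients per arm they can be reviewed by hand, although they are not summaries.

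A reader might therefore infer that no by-arm output shows the size of laboratory changes, or that a liver signal would go unseen. The documents do not support either reading. Nor is the lack of a table by multiples of ULN, or of joint ALT/AST and bilirubin rises, an error: neither document promises one.

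Pooling might also be thought to protect the blind if the SAP is run for an early look. The SAP does not give that reason, and pooling this one table would not achieve it, because the same SAP gives ECG categories, laboratory means and adverse events by arm.

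**Conclusion.** The point holds as a rule in SAP 8.5 that conflicts with the by-arm rules of SAP 8.0 and 9.1 and with the general rule of Protocol 11.7.3. It comes with an omission of minimum and maximum that runs through the SAP and is not particular to laboratory data. Followed as written, the shift table cannot compare either dose with placebo. What is missing by arm is narrow: the separation of new from pre-existing abnormalities among those not judged clinically significant, and the size of individual rises, their peak and their joint occurrence.

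Severity is minor. The text conflict rests on no assumption. The numerical illustrations are arithmetically exact or are stated bounds, but they rest on assumed counts and ALT values; the documents give no expected shift rate, so they show what pooling could hide and do not estimate a loss.

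**What to change.** In SAP 8.5, present the shift tables by treatment arm with a total column, and restore minimum and maximum by arm for laboratory values and changes. The same restoration in SAP 5.0, 6.0, 8.0, 8.3 and 9.1 would bring the whole SAP into line with Protocol 11.4.1. If the SAP is run mid-trial, keep the by-arm outputs with the unblinded statistician named in Protocol 11.8.

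An optional addition, which corrects no error, is one by-arm table of each patient's worst post-baseline ALT, AST, ALP and total bilirubin by multiples of the reporting laboratory's ULN. Cut-offs should be set before unblinding, scheduled and unscheduled samples used, and the count with ALT or AST and bilirubin both raised included.

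The cost is SAP wording, a regrouped table and, if the option is taken, one more output. No new data are needed: Protocol 12.2 already obtains each laboratory's normal values.

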In the 13-week repeat dose GLP study in Beagle dogs, doses of 0 (vehicle), 10 mg/kg BID, 30 mg/kg BID, or $60 \rightarrow 50 \rightarrow 40$ mg/kg BID were utilized. Due to observed toxicity, the dosage of the high dose group (Group 4) was reduced from 60 mg/kg BID to 50 mg/kg BID on Day 8 for both sexes, and then further reduced to 40 mg/kg BID from Day 34 after a 5-day dosing holiday from Day 29 to Day 33. It is referred as $60 \rightarrow 50 \rightarrow 40$ mg/kg BID group. There was no mortality in the study. At 10 mg/kg BID and 30 mg/kg BID dose groups, there were no adverse clinical signs or changes in body weight and food consumption. The observed clinical signs at 10 and 30 mg/kg BID dose group were either transient or of lower magnitude. At $60 \rightarrow 50 \rightarrow 40 \text{ mg/kg BID}$ dose, AUR101 related clinical signs included inappetence, prostration, decreased activity, salivation, thinness, tremors, cold to touch, unkempt fur, abnormal stool, vomitus, ocular discharge, ptosis, and/or pale gums during the dosing period, but were resolved at the end of the recovery period. Increases in liver enzymes (AST/ALT) occurred at 30 mg/kg BID as well as at $60 \rightarrow 50 \rightarrow 40$ mg/kg BID. However, the increase at 30 mg/kg BID was mild and reversible and considered non-adverse. The majority of clinical signs noted at $60 \rightarrow 50 \rightarrow 40 \text{ mg/kg}$ BID as well as increase in liver enzymes in this dose group were considered adverse due to the high frequency and/or severity. Consequently, the no-observed-adverse-effect level (NOAEL) in dogs is considered to be 30 mg/kg/dose BID (i.e. 60 mg/kg/day).

In addition to above toxicology studies, the genetic toxicity assessment of AUR101 has also been investigated. Results of an *in vitro* Bacterial Reverse Mutation Test have indicated that AUR101 is non-mutagenic. Similarly, the results of an *in vivo* micronucleus test in Wistar rats and *in vitro* chromosomal aberration test in human peripheral lymphocytes have indicated that AUR101 does not induce clastogenicity.

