The study did not reveal any clinically relevant hepatic, renal, cardiac, respiratory, or neurological adverse events at any of the dosages in SAD. MAD and Comparative PK cohorts. There is no evidence of any remarkable effect of AUR101 on any clinical laboratory parameters, including hemoglobin, blood counts, liver function or kidney function or on ECG, vitals or physical examination. There were two cases of altered liver function parameters, one occurred in placebo treated subject (Grade 2) in MAD cohort and the other one in comparative PK part with open label AUR101 film coated tablet (Grade 1). Both of these events were deemed as related by the investigator, resolved and did not require any intervention. There were no Grade 3 or higher AEs or serious adverse events (SAEs) or any interruption or discontinuation of the study drug due to AE.

Most commonly reported non-catheter associated Treatment-Emergent Adverse Events (TEAEs; reported ≥ 2 subjects receiving any dose of AUR101 or placebo) in SAD part were fatigue, headache, dizziness, nausea, vomiting, arthralgia, cough and backpain. In MAD part, most commonly reported non-catheter associated TEAEs were headache, abdominal pain, abdominal distension, abdominal discomfort, diarrhea and back pain. In comparative PK part, only headache was reported in ≥ 2 subjects. All of the AEs were mild to moderate in nature and resolved to the satisfaction of the PI. There was no relevant difference between placebo and the AUR101 arms with respect to the nature, severity or frequency of AEs. There is also no pattern or relationship of AEs with AUR101 dose, schedule or formulation.

The study findings from SAD cohorts also confirm that AUR101 is primarily absorbed in the stomach and minimal from intestine. Moreover, food increases the exposure by \sim 2.5 times, further re-confirming that retention of AUR101 in stomach leads to increased absorption.

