7.2 Exclusion Criteria

- 1. History of erythrodermic, guttate, or pustular psoriasis within last 12 months
- 2. Efficacy failure on any biologic (e.g. IL-17 antibodies like brodalumab or ixekizumab or anti-TNF agents. like etanercept, infliximab or adalimumab) for the treatment of psoriasis

Note: Efficacy failure is defined as: A) Failure to achieve static Physician/Investigator Global Assessment (PGA/IGA) of 0 to 2 (i.e. clear to mild) despite a continuous treatment with biologic at the approved (as in package insert) dose for at least 8 weeks B) After having an efficacious response, PGA/IGA increased to 3 or higher while receiving the approved (as in package insert) dose as maintenance

- 3. Static 5-point IGA mod 2011 scale of 0 to 2 at screening or Day 1.
- 4. BMI \geq 35 kg/m2
- 5. Current treatment or history of treatment for psoriasis with IL-17 or IL-12/23 antagonist biological agents (e.g. secukinumab, briakinumab, tildrakizumab, ustekinumab etc.) within 6 months prior to study day 1
- 6. Current treatment or history of treatment for psoriasis with other biological agents (e.g. adalimumab, etanercept, infliximab, alefacept etc.) within 3 months prior to study day 1
- 7. Current treatment or history of treatment for psoriasis with non-biological systemic medications (including systemic steroids, methotrexate, cyclosporine etc.) or phototherapy within 4 weeks prior to study day 1.
- 8. Treatment with medicated topical agents (having active pharmaceutical ingredient that can impact the interfere with effect of the study drug; See section 8.11) within 2 weeks prior to study day 1
- 9. History or presence of any medical or psychiatric disease, or clinically significant laboratory / ECG abnormalities at screening, any or a combination of illnesses, which, in the opinion of the PI, may either put the patient at risk because of participation in the study, or influence the results or the patient's ability to participate in the study.
- 10. Evidence of organ dysfunction (e.g. liver dysfunction ≥ 1.5 X of ULN for ALT, AST or ALP or Total Bilirubin, or renal dysfunction of 1.5X of ULN of serum creatinine)
- 11. Any surgery requiring general anesthesia within 3 months prior to screening
- 12. Known or suspected history of alcoholism or drug abuse, as judged by the investigator
- 13. History or presence of malignancy except patients with non-melanoma skin cancer or carcinoma in situ of cervix who are allowed to participate in the study

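### SAP 8.5 pools the laboratory shift tables over all three arms, so the only planned change-of-category laboratory summary cannot compare AUR101 with placebo or 600 mg with 400 mg

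*SAP*

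**What the plan says.** SAP 8.5 covers haematology, liver function and renal function. It gives counts and percentages for categorical variables and continuous statistics by groups. It then adds that a change from baseline in terms of normal or abnormal findings, clinically significant or not, will also be reported through "shift tables for overall data without mentioning the groups".

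Three other parts of the SAP point the other way:

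- **SAP 8.0** covers all safety parameters and names the laboratory: "Laboratory evaluations) will be summarized descriptively and by treatment".
- **SAP 9.1** sets the general convention: "All data will be presented by treatment group". It mentions an overall column as something added to the treatment groups.
- **SAP 8.4** uses the same three categories (normal, abnormal not clinically significant, abnormal clinically significant) for the ECG: "The ECG data will be analyzed by treatment groups at each visit".

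Protocol 11.7.3 also has laboratory results summarised by treatment group, although it does not ask for shift tables.

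**The concern.** Safety of two doses is a secondary objective (protocol 4.2). Protocol 3.4.1 justifies the second dose by the risk-benefit information it gives for choosing the Phase III dose. SAP 8.0 plans no formal testing of safety data, so the side-by-side display is itself the comparison. A shift table with the arms removed gives none.

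Liver enzymes show why this is more than a formatting point. In the 13-week dog study ALT and AST rose at two dose levels. At the lower one, "the increase at 30 mg/kg BID was mild and reversible and considered non-adverse"; at the higher one the rise was considered adverse (protocol 3.2.3). The human evidence is balanced. Phase I had two liver-function events: "one occurred in placebo treated subject (Grade 2) in MAD cohort and the other one in comparative PK part", the latter Grade 1 on the AUR101 film-coated tablet, with no remarkable effect on liver function overall (protocol 3.3). However, 600 mg BID was given there for 14 days, and here dosing runs for 12 weeks.

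**Working it through.** The plan states no figure on this point. The check is a comparison of texts, followed by an illustration of what a pooled count can hide.

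**1. Is there a conflict?** The wording of SAP 8.5 is explicit. It follows directly on a sentence that gives other laboratory statistics by groups, so a programmer would read it as a deliberate contrast and pool. SAP 8.0 and 9.1 require the opposite, and the SAP gives no reason for an exception. Blinding does not supply one. Protocol 11.8 keeps the study team and sponsor blinded to individual patients at an interim analysis. An arm-level shift table reveals no more than the by-arm ECG, adverse-event and efficacy tables planned in the same SAP.

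**2. Does another planned output show the same thing by arm?**

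| Planned output | By arm? | Shows change of category from baseline per patient? |
|---|---|---|
| Continuous summaries (SAP 8.5) | Yes | No |
| Mean change from baseline (SAP 8.5) | Yes, under SAP 8.0 and 9.1 | No; a few individual rises can be lost in a mean |
| Abnormal values split by clinical significance (SAP 5.4) | Yes, under SAP 8.0 and 9.1 | No; status at a visit only |
| Adverse-event tables (SAP 8.1) | Yes | Only for values judged clinically significant |
| Listings with out-of-range flags (protocol 11.7.3) | Patient level | Only if rebuilt by hand |
| Shift tables (SAP 8.5) | **No** | Yes |

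The adverse-event route comes from protocol 11.7.3: "Laboratory values deemed clinically significant by the Investigator should be reported as AEs". A shift not judged clinically significant need not appear there.

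**3. Can counts of abnormal values stand in for a shift table?** Not fully. Exclusion 10 bars "liver dysfunction ≥ 1.5 X of ULN for ALT, AST or ALP or Total Bilirubin". A patient between 1 and 1.5 times ULN can therefore enter already abnormal. A later abnormal count mixes such patients with new abnormalities, and equal counts at baseline and week 12 can be the same patients or different ones.

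**4. What does a pooled count leave open?** Inputs: about 90 patients randomised 1:1:1 (protocol synopsis), so about 30 per arm. The number of patients who shift, k, is assumed.

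- Pooled rate = k/90.
- Arm splits that fit = number of non-negative triples (400 mg, 600 mg, placebo) with sum k = (k+1)(k+2)/2. The cap of 30 per arm does not bind for these k.
- Largest 600 mg minus placebo difference, in either direction = k/30. By symmetry the same range holds for 600 mg minus 400 mg.

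| k (assumed) | Pooled rate | Arm splits that fit | Range of difference |
|---|---|---|---|
| 3 | 3/90 = 3.3% | 4×5/2 = 10 | -10 to +10 points |
| 6 | 6/90 = 6.7% | 7×8/2 = 28 | -20 to +20 points |
| 9 | 9/90 = 10.0% | 10×11/2 = 55 | -30 to +30 points |

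At k = 9, in the order placebo, 400 mg, 600 mg, the splits 3/3/3, 0/3/6 and 0/0/9 all print as 10.0%. The two-sided Fisher p-values for 600 mg against placebo would be 1.00, 0.024 and 0.002. They are given only to show how different these patterns are, since no safety test is planned.

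**The case against.** The strongest reply is that little is lost. Clinically significant changes become adverse events and are tabulated by dose. SAP 5.4 summarises abnormal values by clinical significance, and SAP 8.0 and 9.1 put that summary by arm. A systematic dose-related rise in ALT or AST would show in mean change. Exclusion 9 also removes patients whose clinically significant screening abnormalities the investigator considers a risk or likely to influence the results, so those who enter abnormal should mostly be in the not-significant category. Blood is drawn at screening and Day 1, so baseline and later counts can be set side by side in each arm. Randomisation balances baseline abnormality in expectation. The shift table is an extra display that the protocol does not require. The ranges above are extremes on assumed counts, and the other by-arm outputs would rule out many of the splits.

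Most of this stands as a limit on the size of the problem. It reduces the loss to individual transitions, mainly from normal to abnormal but not clinically significant, and back. It does not remove the contradiction. Net change in counts is not the same as patient-level transition, and a specific sentence that overrides a general rule without a reason is exactly the one a programmer will follow.

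**Conclusion.** The concern holds. The pooling instruction in SAP 8.5 contradicts SAP 8.0 and 9.1, departs from the handling of the same categories in SAP 8.4, and is out of line with the by-group intent of protocol 11.7.3. The conclusion rests on the texts alone. The counts of 10, 28 and 55 splits are exact for the assumed k and 30 per arm, but they describe what the pooled table by itself leaves open and do not predict this trial's data.

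Importance is low to moderate. By-arm laboratory data are not absent, and the adverse-event data are not affected. The correction should still be made, because it restores a safety comparison that serves a stated objective.

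**What to change.** In SAP 8.5, replace the phrase that calls for pooled shift tables with: *by treatment group (400 mg BID, 600 mg BID, placebo), with a total column*.

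The cost is that one phrase and an arm variable in the table program. The table becomes about three times as wide and its cells are small, with about 30 patients per arm, so it should be read descriptively. No test is added.
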